5.8.1 Hemodialysis Parameters

Hemodialysis parameters consist of normal saline prime, normal saline bolus, normal saline rinse back, initial fluid removal goal, total fluid removal goal, total fluid output, Kt/V, blood flow rate, dialysate flow rate, arterial pressure, venous pressure, ultrafiltration rate, TMP, dialysate Temp, oxygen Sat pre-dialysis, oxygen Sat post-dialysis, sodium pre-dialysis, sodium post-dialysis, bicarbonate, hematocrit pre-dialysis, hematocrit post-dialysis, estimated dry weight, type of dialyzer, consciousness, eyes open, best verbal response, best motor response, respirations, lungs, lung ultrasound monitoring of Kerley B-line The hemodialysis parameters will be summarized by visit and treatment period.

Additionally, URR (%) will be summarized. URR (%) is calculated as:

$$\text{URR (\%)} = (1 - \text{postdialysis BUN} / \text{predialysis BUN}) \times 100$$

A listing of hemodialysis will be provided (included in DSMB).

5.8.2 Fluid Assessments

Fluid Assessments will not be summarized but will be provided as a listing.

5.8.3 Heparin Infusion

The amount of heparin used in each HD session in each treatment period will be summarized by column size (AKST1210 S-15, S-25, and S-35) and overall.

5.8.4 Study Device Accountability

Study Device Accountability will not be summarized but will be provided as a listing.

5.8.5 Adverse Events

All AEs that occur after the time of treatment with the study device will be considered TEAEs and will be reported. Events meeting this definition will be those events that are a change from subject's baseline condition, including an increase in frequency or severity (these will be entered as new AEs). For AEs occurring on the date of first treatment, if the time of onset is missing, the AE will be assumed to be treatment emergent.

All AEs, TEAEs, and SAEs will be coded using the MedDRA Version 23.0 or higher coding dictionary. The AE analyses will focus on those that are treatment emergent; however, any AEs that are reported after consent has been signed and before initial treatment, will be considered intercurrent events and flagged in the listings as such.

The causal relationship of the AE to the study device is determined by the investigator as Unrelated, Possibly Related, or Definitely Related. These can be

mapped to Unrelated (*Unrelated*) or Related (*Possibly Related or Definitely Related*). Adverse event summaries will be repeated for treatment-related TEAEs.

Adverse events severity grade will be reported as mild, moderate, or severe.

Summaries of incidence rates (frequencies and percentages) of individual TEAEs will be presented by SOC, PT, and treatment group. Such summaries will be displaced for all TEAEs, TEAEs maximum severity, and TEAEs by relationship.

Each subject will be counted only once within each summation level (SOC and PT). If a subject experience more than 1 TEAE within each summation level only, the TEAE with the strongest relationship or the maximum severity, as appropriate, will be included in the summaries of relationship and severity. If a particular event is missing the severity and/or relationship, then the strongest possible severity or relationship will be assumed for analysis (severity=severe, relationship=definitely related).

Per ISO 14155:2011, an adverse device effect (ADE) is an AE that is assessed as possibly or definitely related to the use of an investigational medical device:

- Note 1: This definition includes AEs resulting from insufficient or inadequate instructions for use, deployment, implantation, installation, or operation, or any malfunction of the investigational medical device.
- Note 2: This definition includes any event resulting from use error or from intentional misuse of the investigational medical device.

Per ISO 14155:2011 a serious adverse device effect (SADE) is an ADE that results in any of the consequences characteristic of an SAE.

Per 21 CFR 812.3(s) an unanticipated adverse device effect (UADE), “means any serious adverse effect on health or safety or any life-threatening problem or death caused by, or associated with, a device, if that effect, problem, or death was not previously identified in nature, severity, or degree of incidence in the investigational plan or application (including a supplementary plan or application), or any other unanticipated serious problem associated with a device that relates to the rights, safety, or welfare of subjects.”

The investigator is required to make an initial assessment of whether a SADE is considered anticipated according to the known risks and associated device effects identified in Section 2.3.1 and the AKST1210 Investigator’s Brochure. If a SADE is considered unanticipated by the investigator, it must be reported to the Sponsor or designee.

A summary of all TEAEs, as reported in the EDC, by the number and percentages of subjects who experienced any of the following will be provided:

- Any TEAE, including severity (Mild, Moderate, and Severe), relationship to study treatment (Unrelated, Possibly Related, Definitively Related), AEs leading to discontinuation of study participation.
- Any serious TEAE, including severity (Mild, Moderate, and Severe), relationship to study treatment (Unrelated, Possibly Related, Definitively Related), AEs leading to discontinuation of study participation
- Any fatal TEAEs, including relationship to study treatment (Unrelated, Possibly Related, Definitively Related)

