8.2.2 RELATIONSHIP TO STUDY DEVICE

Investigators are required to assess relatedness (i.e., whether there is reasonable possibility that the study device caused the event) using the following definitions:

- Unrelated: another cause of the AE is more plausible; a temporal sequence cannot be established with the onset of the AE and administration of the study device; or a causal relationship is considered biologically implausible.
- Possibly Related: There is a clinically plausible time sequence between onset of the AE and administration of the study device, but the AE could also be attributed to concurrent or underlying disease, or the use of other devices or procedures. Possibly related should be used when the study device is one or several biologically plausible AE causes.
- Definitely Related: The AE is clearly related to use of the study device.

If either the investigator or the Sponsor considers the event related, then the event will be considered related for reporting purposes and will therefore be an ADE or SADE.

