8.2.3 EXPECTEDNESS OF ADVERSE DEVICE EFFECTS**8.2.3.1 Unanticipated Adverse Device Effect**

Per 21 CFR 812.3(s) an unanticipated adverse device effect (UADE), “means any serious adverse effect on health or safety or any life-threatening problem or death caused by, or associated with, a device, if that effect, problem, or death was not previously identified in nature, severity, or degree of incidence in the investigational plan or application (including a supplementary plan or application), or any other unanticipated serious problem associated with a device that relates to the rights, safety, or welfare of subjects.”

The investigator is required to make an initial assessment of whether an SADE is considered anticipated according to the known risks and associated device effects identified in [Section 2.3.1](#) and the [AKST1210 Investigator's Brochure](#). If an SADE is considered unanticipated by the investigator, it must be reported to the Sponsor or designee according to the timeframes outlined in [Section 8.4.2.1](#). Once received, the Sponsor or designee will be responsible for making the final determination of whether the device effect is unanticipated for subsequent reporting to FDA.

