5.8.5.1 Summary for All TEAEs

The number and percentage of subjects who experience TEAEs will be tabulated by SOC and PT using MedDRA dictionary version 23.0. Adverse events will be counted only once for a subject within each PT and SOC. Since a subject may have more than one PT within a SOC, percentages of PT may not sum to the percentages in the SOC (included in DSMB report).

Incidences will be presented by descending frequency of SOC and PT within SOC, and then alphabetically within PT where the incidence is same; this is based on overall subjects then alphabetically in case of a tie.

Missing and partially missing AE start and/or stop dates will be imputed, for the purpose of statistical analysis. All collected data will be presented in listings. Data not subject to analysis according to this plan will not appear in any tables or graphs but will be included only in the data listings.

Adverse events will be coded using the MedDRA version 23.0 or higher.

A treatment related AE is any AE with a relationship to the study device of possibly related or definitely related.

For all TEAEs the following will be summarized:

- Overall summary of any TEAEs presented by SOC/PT
- Overall summary of any TEAEs by worst severity presented by SOC/PT
- Overall summary of any TEAEs by most causal relationship presented by SOC/PT
- Overall summary of any ADE/SADE/UADEs

A Listing of all AEs will be provided. This listing will include a flag identifying if an AE is a TEAE.

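### The SAP names only the investigator as the source for its ADE/SADE/UADE table, while the protocol also counts the Sponsor's assessment, so ADE and SADE counts could be too low

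*SAP*

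**What the plan says.** **Protocol.** Section 8.2.2 asks investigators to grade relatedness and then adds a second assessor: "If either the investigator or the Sponsor considers the event related, then the event will be considered related for reporting purposes". The sentence ends with a classification: "and will therefore be an ADE or SADE". On unanticipated effects, section 8.2.3.1 has the investigator make an initial assessment, after which "the Sponsor or designee will be responsible for making the final determination of whether the device effect is unanticipated". That sentence goes on to tie the determination to later FDA reporting.

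**SAP.** Section 5.8.5 states: "The causal relationship of the AE to the study device is determined by the investigator", on three grades (unrelated, possibly related, definitely related). It collapses these three grades to related or unrelated and repeats the adverse event summaries for related TEAEs. Its definition of a device effect is that "an adverse device effect (ADE) is an AE that is assessed as possibly or definitely related to the use of an investigational medical device"; that sentence names no assessor. Section 5.8.5.1 words treatment-relatedness the same way: "A treatment related AE is any AE with a relationship to the study device of possibly related or definitely related". On unanticipated effects, section 5.8.5 repeats the investigator's initial assessment and the duty to report to the Sponsor, and goes no further. Section 5.8.5.1 then lists among its outputs "Overall summary of any ADE/SADE/UADEs".

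The SAP nowhere mentions a Sponsor causality assessment or the either-assessor rule.

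**The concern.** The two documents use different rules for the same labels. Under the protocol, a Sponsor-only judgement of related is enough to make an event an ADE or SADE. Under the SAP, the only relatedness variable described is the investigator's, so a programmer has nothing else from which to build the flag.

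Safety and tolerability is the primary objective, and the ADE/SADE/UADE table is where a reader of the study report would look for the device's own harms. If the Sponsor upgrades an event, that event is a device effect under the protocol but absent from the table. For UADEs, the SAP does not say whether the table counts the investigator's initial view or the Sponsor's final one, and these can differ.

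**Working it through.** The plan states no figure on this point, so there is none to reproduce. The check is a comparison of rules, then a scale for one subject.

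**1. Which rule sets each label**

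| Label | Protocol | SAP |
|---|---|---|
| ADE, SADE | Investigator or Sponsor (8.2.2) | Possibly or definitely related; the only assessor named for that variable is the investigator (5.8.5) |
| UADE | Investigator first, Sponsor final for FDA reporting (8.2.3.1) | Investigator's initial assessment only (5.8.5) |
| Related TEAE in tables | Attribution is to be shown, assessor not named (10.4.2) | Investigator (5.8.5) |
| Any TEAE, any SAE | Does not use relatedness (4.2.1) | Does not use relatedness (3.1; tests in 5.8.5.2) |

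**2. Direction for ADE and SADE.** Let I be the set of events the investigator calls related and S the set the Sponsor calls related.

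- Protocol set: I or S.
- SAP set as written: I.
- Difference: events in S but not in I, a count of zero or more.

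The SAP count is therefore equal to or below the protocol count, never above it. In a table of subjects, a person is lost only if they have no investigator-related event at the same level of the table.

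**3. Direction for UADE.** The Sponsor can call unanticipated an effect that the investigator thought anticipated, or the reverse. The Sponsor's count minus the investigator's count equals upgrades minus downgrades, which can have either sign.

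**4. Do the SAP's other rules close the gap?** Section 5.8.5 sets a missing relationship to definitely related, and takes the strongest relationship when a subject has several events at one level. The first acts on blanks and the second works across a subject's events. Neither deals with one event graded unrelated by one assessor and related by the other.

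**5. Scale.** Safety tables use the Safety population (SAP 5.2.2). Assume that all 26 planned subjects are randomized 1:1 and treated, so 26 / 2 = 13 per arm. The number of subjects k in an arm whose only related event is a Sponsor-only call is not in the documents; 0 to 3 is an assumed range. The shortfall is 100 × k / 13:

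- k = 0: 0 points
- k = 1: 7.7 points
- k = 2: 15.4 points
- k = 3: 23.1 points

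These figures show what a subject weighs in the table. They say nothing about how likely an upgrade is.

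**The case against.** The case on the other side has several parts, and some of it stands.

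- **The protocol rule is limited to reporting.** It sits in the safety section and may mean reports to the Sponsor, IRB and FDA, not study tables. Protocol 10.4.2 asks for attribution without saying whose. This stands for the related-TEAE tables: a reader might infer that investigator attribution there breaches the protocol, but the documents do not say so. It does not dispose of the ADE/SADE table, because the same protocol sentence goes on to classify the event, and the SAP tabulates that class. No document sets up one definition for reports and another for tables.
- **The SAP's ADE sentence names no assessor.** True, so investigator-only ADE/SADE flags are an inference. The table shells are separate attachments, not available here, and could name a source. But the grades used in that sentence are those of the one variable the SAP defines, which it assigns to the investigator.
- **Nothing shows that any count will be wrong.** This stands. A reader might infer that the counts would be too low; the documents give no upgrade rate, so they support only that the counts could be. Two rules already lean towards related: assessors assume that the subject received the column (Protocol 8), and the possibly-related grade covers a device that is just one of several plausible causes (Protocol 8.2.2).
- **The primary endpoint is untouched.** This stands. A reader might infer that the primary safety result is under-counted. TEAE and SAE incidence, and the tests on them in SAP 5.8.5.2, do not use relatedness.
- **The error is not one-way for every class.** This stands for UADEs, as step 3 of the working shows.
- **A Sponsor causality field may not exist for every event.** The documents describe forms sent to the Sponsor's side for serious events and no Sponsor grading recorded for each non-serious one. This limits the remedy to the Sponsor assessments that exist.

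**Conclusion.** The point holds for the ADE/SADE/UADE table. The protocol's classification rule and the SAP's named source of relatedness conflict in the current text, and the SAP leaves out the Sponsor's final determination on UADEs. ADE and SADE counts could be too low and cannot be too high; UADE counts could be off in either direction.

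The size cannot be computed. It is zero if the Sponsor upgrades no event; otherwise each subject who drops out of the table for this reason is 7.7 points of an arm's incidence, given 13 treated. The conclusion rests on reading the SAP's ADE definition as drawing on the investigator's variable, the only one it describes. It does not extend to the primary endpoint, and it does not make investigator attribution wrong in the related-TEAE tables. The correction is worth making before database lock because it is cheap and concerns the table that bears most directly on device harm.

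**What to change.** In SAP 5.8.5 and 5.8.5.1:

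1. Set the ADE/SADE flag when either the investigator or the Sponsor assesses the event as possibly or definitely related.
2. Set the UADE flag by the Sponsor's final determination.
3. Name the data source for the Sponsor's assessments, and say for which events they exist.
4. List every event on which the two assessors disagree, showing both assessments.
5. Keep the related-TEAE tables on the investigator's attribution if preferred, with a title or footnote that says so.

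The cost is a few lines of SAP text, one listing, and a small step to reconcile the Sponsor's assessments with the study data. Device-effect counts may come out slightly higher than on the investigator's call alone. No change to the protocol or to data collection at sites is needed, provided that the Sponsor's assessments are already recorded somewhere; the documents do not say where.

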10.4.2 ANALYSIS OF THE PRIMARY ENDPOINT

Safety and tolerability will be evaluated by examining the occurrence of TEAEs and AEs leading to de-escalation and/or discontinuation from the study.

Summary tabulations of the reported AEs will be presented by arm and column size after the verbatim terms have been coded to PTs and SOCs using the MedDRA Version 21.0 coding dictionary. The summaries will include severity and attribution to the study device. Multiple reports of the same AE by the same subject will be counted only once at the highest severity and strongest attribution to the study device.

Additional details are presented in [Section 10.4.4](#).

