5.1 General Considerations

This section presents the statistical approaches that are anticipated for the analysis of the study data. These approaches may at times require modifications due to unanticipated features of the data. Deviations from analyses summarized in this document will be noted in the CSR.

All statistical analyses will be performed using SAS® Version 9.4 or higher, unless otherwise noted. Data will be summarized using descriptive statistics, unless otherwise noted. Number of subjects (n) with non-missing values mean, median, standard deviation, minimum, and maximum will be summarized for continuous (quantitative) variables. Categorical (qualitative) variables will be summarized using frequencies and percentages of subjects who are in a particular category or each possible value. In general, the denominator for the percentage calculation will be based upon the total number of subjects in the study population for each treatment group, unless otherwise specified. The denominator for by-visit displays will be the number of subjects in the relevant study population with non-missing data at each visit. Presentations will be by treatment group (AKST1210 and Control) and Total, unless otherwise noted.

The minimum and maximum will be reported with the same degree of precision (i.e., the same number of decimal places) as the observed data. Measures of location (mean and median) will be reported to 1 degree precision more than the observed data and measures of spread (SD) will be reported to 2 degrees of precision more than the observed data.

Percentages will be presented to 1 decimal place, unless otherwise specified. Percentages will not be displayed when the numerator for a cell is 0.

Unless otherwise indicated, all statistical tests will be conducted at 0.05 significance level using 2-tailed tests, and P values will be reported. Corresponding 95% CIs will be presented for statistical tests.

In general, all summary tables will be supported by a relevant subject data listing including all subjects who are randomized. The listings will include all data collected, and will be sorted by subject ID, and actual visit date, as applicable, unless otherwise noted. The listing will also include the column size for each of the three treatment periods as applicable.

Study day 1 is the first day of HD treatment with AKST1210 or control. Study day is the day relative to the study day 1.

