5.8 Safety Analyses

Safety analyses include hemodialysis parameters, adverse events, laboratory parameters, vital signs, weight, 12-lead electrocardiogram (ECG), physical examination, pregnancy tests, cognitive assessments during IDH and prior and concomitant medications. Except where indicated, safety parameters will be summarized by treatment group (AKST1210 and Control) using the safety population. A subset of the safety tables defined below will also be provided to the

DSMB for their periodic assessment of safety. The DSMB tables are identified within the analysis description.

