5.8.5.2 Summary for serious TEAEs

For all serious TEAEs the following will be summarized (included in DSMB report):

- Overall summary of any serious TEAEs by worst severity presented by SOC/PT
- Overall summary of any serious TEAEs by closest relationship presented by SOC/PT

A listing of all serious AEs will be provided. This listing will include a flag identifying if a serious AE is a TEAE.

A test of hypothesis comparing the proportions of subjects reporting a TEAE throughout the study will be conducted using a Chi-square or Fisher's exact test, as appropriate. The null hypothesis is that there is no difference in proportion between treatment groups, with a two-sided alternative that considers the possibility of a difference in either direction. The number and percentage of subjects reporting a TEAE and the 95% Wilson confidence interval (CI) for the proportion will be presented for each treatment group. In addition, the difference in proportions between the device and control groups and the 95% Wilson CI will be presented. The same statistics and hypothesis testing will be performed for subjects reporting a SAE throughout the study.

All *P* values will be displayed in four decimals and rounded using standard scientific notation (e.g., 0.XXX). If a *P* value less than 0.0001 occurs it will be shown in tables as <0.0001.

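### The protocol's primary safety analysis calls for adverse-event tables by arm and column size; the SAP text plans them by arm only, and its by-size de-escalation count names Treatment Period 3 alone

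*SAP*

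**What the plan says.** Protocol 10.4.2 sets out the analysis of the primary endpoint. On layout it says: "Summary tabulations of the reported AEs will be presented by arm and column size". Among the events to be examined it names "AEs leading to de-escalation and/or discontinuation from the study".

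The SAP was written to the same protocol version (2.1). Its default, in section 5.8, is that "safety parameters will be summarized by treatment group (AKST1210 and Control) using the safety population", except where it indicates otherwise. For adverse events nothing else is indicated. Section 5.8.5 says: "Summaries of incidence rates (frequencies and percentages) of individual TEAEs will be presented by SOC, PT, and treatment group". Section 5.8.5.3 repeats treatment group for TEAEs leading to withdrawal, and 5.8.5.1 and 5.8.5.2 do not mention size.

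Elsewhere the SAP names column size where it wants it. In the same safety section: "The amount of heparin used in each HD session in each treatment period will be summarized by column size". Sections 5.7.2, 5.7.3, 5.7.5 and 5.7.8 also break results down by S-15, S-25 and S-35. For listings, section 5.1 says: "The listing will also include the column size for each of the three treatment periods as applicable".

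On de-escalation, the by-size table in SAP 5.7.2 has a row for subjects stepped down to a smaller column, by reason, and ties it to Treatment Period 3. Sections 5.7.4 and 5.7.6 count IDH and anemia leading to de-escalation or discontinuation without naming a period, by treatment group and Total.

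**The concern.** Column size is the exposure gradient of this trial. Protocol Table 2 gives extracorporeal volumes of 65, 105 and 177 mL for the three models, and the guideline heparin infusion in protocol 7.1.1.1.6.1 rises from 1,000 to 1,500 to 2,000 IU per hour. A safety problem tied to the larger columns is what a by-size tabulation is meant to show, and the protocol placed that tabulation in the primary analysis.

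If the SAP is followed as written, a TEAE or SAE other than IDH or anemia can be related to size only by reading listings. Step-downs from S-25 are also not clearly tabulated against S-25, although tolerability of each size escalation is a secondary endpoint.

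**Working it through.** No figure in the plan needs reproducing for the main point. The check is a comparison of the planned outputs.

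**Step 1: which tables relate clinical events to size, and in whom**

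| Planned table | Population | By column size |
|---|---|---|
| TEAEs by SOC/PT, severity, relationship (SAP 5.8.5, 5.8.5.1) | Safety | No |
| Serious TEAEs (5.8.5.2) | Safety | No |
| TEAEs leading to withdrawal (5.8.5.3) | Safety | No |
| IDH counts and change above historical rate (5.7.3) | Evaluable, PP | Yes |
| Worsening anemia (5.7.5) | Evaluable, PP | Yes |
| IDH or anemia leading to de-escalation or discontinuation (5.7.4, 5.7.6) | Evaluable, PP | No |
| De-escalation by reason (5.7.2) | Evaluable, PP | Yes, Period 3 named |

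The populations of the last four rows follow from the default in SAP 5.7. No row combines the Safety population with column size. AEs leading to withdrawal are tabulated in the Safety population. De-escalation is counted only in the Evaluable and PP populations.

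**Step 2: when step-down can occur.** Treatment Period 1 uses the smallest column, so there is no smaller size to go to. Appendix 17.1 allows de-escalation at any point in a 4-week period. The Period 2 schedule (protocol 15.1.3) monitors for it at every session, and SAP 4.7 lists it for Period 2. Step-down is therefore possible in two of the three periods, and the 5.7.2 row names one of them.

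**Step 3: who is outside the Evaluable by-size tables.** SAP 5.2.3 requires a Week 8 visit. Inputs from protocol 10.5: 26 enrolled, 20% drop-out, about 20 evaluable, 1:1 allocation.
- From the drop-out rate: 26 × 0.20 = 5.2 over both arms; 5.2 / 2 = 2.6 in the active arm.
- From the target: 26 − 20 = 6 over both arms; 6 / 2 = 3 in the active arm.
- Active arm size: 26 / 2 = 13.

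This gives about 2.6 to 3 of 13. It assumes that all 26 are randomized, that drop-out is equal between arms, and that no one has yet been replaced. It is smaller if some of the drop-out falls in Screening or Run-in.

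**Step 4: how much sparse tables can say.** With 0 events among n exposed, the one-sided 95% upper limit for the risk is 1 − 0.05^(1/n).
- n = 10 (planned evaluable per arm): 1 − 0.05^(1/10) = 0.259, or 26%.
- n = 5 (assumed, for a size reached by few): 1 − 0.05^(1/5) = 0.451, or 45%.

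**The case against.** The strongest case on the other side has five parts.

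- **Size is not lost.** A reader might infer that the SAP removes size from the safety data. It does not. Section 5.1 puts size per treatment period in the listings, 5.8.5.1 says "A Listing of all AEs will be provided", 5.8.5.2 says "A listing of all serious AEs will be provided", and 5.8.4 lists device accountability, for which protocol 6.2 records date and column size. This stands. But the protocol asks for tabulations, and for a subject stepped down within a period, one size per period does not by itself give the size at onset.
- **The main size-related risks are already tabulated.** IDH and worsening anemia do appear by size, in the populations that the protocol directs for secondary endpoints. That is consistent with the protocol, but it does not replace Safety-population tables of TEAEs and SAEs.
- **The 5.7.2 wording may mean something else.** SAP 4.7 places a Period 2 evaluation on Day 54, so a step-down decided then would take effect in Period 3. The row may mean subjects on a smaller column during Period 3. The ambiguity is real. A reader might infer that most step-downs would go uncounted. The documents do not support that, because they give no de-escalation or escalation rates and because 5.7.4 and 5.7.6 count IDH and anemia step-downs in any period by arm.
- **Rewording 5.7.2 is not enough.** This is correct. A subject who is stepped down and stops before a Week 8 visit is outside the Evaluable population whatever period the row names.
- **Splitting 5.7.4 and 5.7.6 by size goes beyond the endpoints.** This is also correct. The endpoint wording attaches size to worsening anemia, but not to events leading to de-escalation or discontinuation.

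The table shells are separate attachments and were not available, so the point concerns the SAP text.

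**Conclusion.** The SAP text omits, without explanation, a tabulation that the protocol makes part of the primary safety analysis: TEAEs and SAEs by column size in the Safety population. De-escalation, which protocol 10.4.2 also names, is counted only in the Evaluable and PP populations. The 5.7.2 row, read literally, misses Period 2 step-downs. Its wording is ambiguous and should be settled.

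This should be corrected, but it does not undermine the trial. The arm comparison of adverse events is intact, withdrawals due to TEAEs are tabulated, and the data needed are collected. The one size that can be given is the Evaluable shortfall of about 2.6 to 3 of 13 active-arm subjects, under the assumptions in the working. Taking all 5.2 to 6 of 26 as missing from the by-size tables would overstate it, because only active-arm subjects have a column size.

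**What to change.** 1. **SAP 5.8.5.** Add descriptive TEAE and serious-TEAE tables in the Safety population by column size in use at onset, derived from AE onset dates and dated dispensing records. Use subjects exposed to that size as the denominator and show control alongside. State that size is confounded with time on study and with having tolerated the smaller sizes. If the shells already carry size columns, say so in 5.8.5 instead. If the departure from protocol 10.4.2 is intended, justify it.
2. **SAP 5.7.2.** Extend the de-escalation row to Treatment Periods 2 and 3, by the size stepped down from and by reason, and present it in the Safety population as well.
3. **SAP 5.7.4 and 5.7.6.** Repeat both in the Safety population, to cover adverse events leading to de-escalation. This matters because the AE action-taken field in protocol 8.4.1 has no de-escalation category, so the AE form alone does not identify them. A breakdown by size here is optional.

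The cost is a few extra tables and one wording change, with no new data. The tables will be sparse: no events is compatible with a risk of up to 26% with 10 exposed and up to 45% with 5. They should be labelled as description and carry no tests.
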